7.5 Tumor Imaging

CT scan of the chest, abdomen, and pelvis will be obtained at baseline. Then for each course of MK-3475 it will be obtained during the 3rd week of cycles 2 and 4, and then every 4 cycles thereafter (e.g., cycles 8, 12, etc). Additional re-imaging may be obtained at the discretion of the investigator. A PET/CT may be substituted for CT of the chest, abdomen, and pelvis if clinically appropriate. In the event the patient's insurance denies part of the scan (e.g. only CT of the chest is approved), the Principal Investigator or patient's treating physician may waive part of the imaging requirement, or adjust the timing of imaging as medically necessary.

7.6 Study Assessments

Informed Consent

The Investigator must obtain documented consent from each potential subject prior to participating in a clinical trial.

Consent must be documented by the subject's dated signature or by the subject's legally acceptable representative's dated signature on a consent form along with the dated signature of the person conducting the consent discussion.

A copy of the signed and dated consent form should be given to the subject before participation in the trial.

The initial informed consent form, any subsequent revised written informed consent form and any written information provided to the subject must receive the IRB/ERC's approval/favorable opinion in advance of use. The subject or his/her legally acceptable representative should be informed in a timely manner if new information becomes available that may be relevant to the subject's willingness to continue participation in the trial. The communication of this information will be provided and documented via a revised consent form or addendum to the original consent form that captures the subject's dated signature or by the subject's legally acceptable representative's dated signature.

Inclusion/Exclusion Criteria

All inclusion and exclusion criteria will be reviewed by the investigator or qualified designee to ensure that the subject qualifies for the trial.

Medical History

A medical history will be obtained by the investigator or qualified designee. Medical history will include all active conditions, and any condition diagnosed within the prior 10 years that are considered to be clinically significant by the Investigator. Details regarding the disease for which the subject has enrolled in this study will be recorded separately and not listed as medical history.

Prior and Concomitant Medications Review

Prior Medications

The investigator or qualified designee will review prior medication use, including any protocol-specified washout requirement, and record prior medication taken by the subject within 28 days before starting the trial. Treatment for the disease for which the subject has enrolled in this study will be recorded separately and not listed as a prior medication.

Full Physical Exam

The investigator or qualified designee will perform a complete physical exam during the screening period. Clinically significant abnormal findings should be recorded as medical history. A full physical exam should be performed during screening.

Directed Physical Exam

For cycles that do not require a full physical exam per the Trial Flow Chart, the investigator or qualified designee will perform a directed physical exam as clinically indicated prior to trial treatment administration.

Vital Signs

The investigator or qualified designee will take vital signs at screening, prior to the administration of each dose of trial treatment and at treatment discontinuation as specified in the Trial Flow Chart (Section 6.0). Vital signs should include temperature, pulse, respiratory rate, weight and blood pressure. Height will be measured at screening only, or taken from the subject's medical record.

Eastern Cooperative Oncology Group (ECOG) Performance Scale

The investigator or qualified designee will assess ECOG status (see Section 12.4) at screening, prior to the administration of each dose of trial treatment and discontinuation of trial treatment as specified in the Trial Flow Chart. After Cycle 8 assessment of ECOG status will be performed every other cycle in conjunction with the directed or full physical exam.

Tumor Tissue Collection and Correlative Studies Blood Sampling

Before and during trial therapy, if an irradiated or unirradiated lesion is biopsied or resected for clinical purposes, a sample will be retained for protocol-related correlative studies. After tissue is obtained, it will be subjected to flash freezing in liquid nitrogen and SNAP frozen tissue will be stored for further studies. If a patient has had a previous biopsy, the pre-treatment sample may be taken from paraffin-embedded tissue.

Laboratory Procedures/Assessments

Details regarding specific laboratory procedures/assessments to be performed in this trial are provided below. The total amount of blood/tissue to be drawn/collected over the course of the trial (from pre-trial to post-trial visits), including approximate blood/tissue volumes drawn/collected by visit and by sample type per subject can be found in the Procedures Manual.

Laboratory Safety Evaluations (Hematology, Chemistry and Urinalysis)

The total amount of blood/tissue to be drawn/collected over the course of the trial (from pre-trial to post-trial visits), including approximate blood/tissue volumes drawn/collected by visit and by sample type per subject can be found in the Procedures Manual.

Study-Related Biopsies and Tissue Collection

Tissue from fresh or archival tissue (see below) is required at study entry. When a biopsy is being done for standard-of-care clinical purposes, tissue will be obtained from this procedure, if available.

Tumor tissue will be obtained prior to initiation of study therapy from any primary or metastatic site and processed according to the specifications of the lab manual. At the discretion of the principal investigator, archival tissue may be used in place of a fresh biopsy.

8.0 ADVERSE EVENT REPORTING

Evaluating Adverse Events

An investigator who is a qualified physician will evaluate all adverse events according to the NCI Common Terminology for Adverse Events (CTCAE), version 4.0. Any adverse event which changes CTCAE grade over the course of a given episode will have each change of grade recorded on the adverse event case report forms/worksheets.

All adverse events regardless of CTCAE grade must also be evaluated for seriousness.

8.1 Definitions

An adverse event is defined as any untoward medical occurrence in a patient or clinical investigation subject administered a pharmaceutical product and which does not necessarily have to have a causal relationship with this treatment. An adverse event can therefore be any unfavorable and unintended sign (including an abnormal laboratory finding, for example), symptom, or disease temporally associated with the use of a medicinal product or protocol-

specified procedure, whether or not considered related to the medicinal product or protocol-specified procedure. Any worsening (i.e., any clinically significant adverse change in frequency and/or intensity) of a preexisting condition that is temporally associated with the use of the trial therapy, is also an adverse event.

Changes resulting from normal growth and development that do not vary significantly in frequency or severity from expected levels are not to be considered adverse events. All adverse events that after the consent form is signed but before treatment allocation must be reported by the investigator if they cause the subject to be excluded from the trial, or are the result of a protocol-specified intervention, including but not limited to washout or discontinuation of usual therapy, diet, placebo treatment or a procedure.

Adverse events will not be collected for subjects during the pre-screening period (for determination of archival tissue status) as long as that subject has not undergone any protocol-specified procedure or intervention. If the subject requires a fresh tumor biopsy, the subject is first required to provide consent to the main study and AEs will be captured according to guidelines for standard AE reporting.

Serious Adverse Events

A serious adverse event is any of the following:

- Death
- Any adverse event which is life threatening;
- Any adverse event leading to persistent or significant disability/incapacity;
- Any adverse event which results in or prolongs an existing inpatient hospitalization;
- A congenital anomaly/birth defect as a result of trial therapy;
- Any other important medical event
- Pregnancy

Note: In addition to the above criteria, adverse events meeting either of the below criteria, although not serious per ICH definition, are reportable to the Merck in the same timeframe as SAEs to meet certain local requirements. Therefore, these events are considered serious by Merck for collection purposes.

- Is a new cancer (that is not a condition of the study);
- Is associated with an overdose.

Important medical events that may not result in death, be life-threatening, or require hospitalization may be considered a serious adverse drug experience when, based upon appropriate medical judgment, they may jeopardize the patient or subject and may require medical or surgical intervention to prevent one of the outcomes listed in this definition. [21CFR312.32(a)]. Hospitalization related to convenience (e.g., transportation issues, etc.) will not be considered a SAE.

Progression of the cancer under study is not considered an adverse event.

“Serious” Versus “Severe” Adverse Events: There is a distinction between serious and severe AEs. Assessment of seriousness will be made solely by the serious criteria listed above. Severity of AEs will be graded according to the NCI Common Terminology Criteria for Adverse Events v4.0. Therefore, serious events will not be automatically considered severe. For example, a stroke that results in only a limited degree of disability may be considered a mild (not severe) stroke, but it would still meet serious criteria and thus, be captured as an SAE. Similarly, severe events may not always be serious. An example would be an episode of severe, transient nausea which persists for several hours. This would be classified as a “severe” episode of nausea, but if it did not require treatment, intervention, or somehow meet other serious criteria, it would not be considered an SAE.

Duration of Reporting of SAEs: From the administration of first treatment until 30 days (unless otherwise specified) subsequent to last treatment or withdrawal of subject, new onset adverse events will be captured. Follow-up and reporting of these events will follow the same procedure as for AEs observed during the study period. In addition, any unexpected Serious Adverse Event that occurs more than 90 days after drug administration but is possibly, probably or definitely attributed to drug administration will be recorded and reported.

Life-threatening Adverse Drug Experience: Any adverse drug experience that places the patient or subject, in the view of the investigator, at immediate risk of death from the reaction as it occurred, i.e. it does not include a reaction that, had it occurred in a more severe form, might have caused death. [21CFR312.32(a)]

Unexpected Adverse Drug Experience: Any adverse drug experience, the specificity or severity of which is not consistent with the current investigator brochure; or, if an investigator brochure is not required or available, the specificity or severity of which is not consistent with the risk information described in the general investigational plan. “Unexpected” as used in this definition, refers to an adverse drug experience that has not been previously observed (e.g., included in the investigator brochure) rather than from the perspective of such experience not being anticipated from the pharmacological properties of the pharmaceutical product.[21CFR312.32(a)]

Events of Clinical Interest:

Selected non-serious and serious adverse events are also known as Events of Clinical Interest (ECI) and must be recorded as such on the Adverse Event case report forms/worksheets and reported within 24 hours to the Sponsor-Investigator and within 2 working days to Merck Global Safety. (Attn: Worldwide Product Safety; [contact]).

For the time period beginning when the consent form is signed until treatment allocation/randomization, any ECI, or follow up to an ECI, that occurs to any subject must be reported within 24 hours to the Sponsor-Investigator and within 2 working days to Merck Global Safety if it causes the subject to be excluded from the trial, or is the result of a protocol-specified intervention, including but not limited to washout or discontinuation of usual therapy, diet, placebo treatment or a procedure.

For the time period beginning at treatment allocation/randomization through 90 days following cessation of treatment, or 30 days following cessation of treatment if the subject initiates new

anticancer therapy, whichever is earlier, any ECI, or follow up to an ECI, whether or not related to Merck product, must be reported within 24 hours to the Sponsor-Investigator and within 24 hours to Merck Global Safety.

Events of clinical interest for this trial include:

- an overdose of Merck product. For the purposes of this trial, an overdose will be defined as any dose exceeding the prescribed dose for MK-3475 by 20% over the prescribed dose.
- an elevated AST or ALT lab value that is greater than or equal to 3X the upper limit of normal and an elevated total bilirubin lab value that is greater than or equal to 2X the upper limit of normal and, at the same time, an alkaline phosphatase lab value that is less than 2X the upper limit of normal, as determined by way of protocol-specified laboratory testing or unscheduled laboratory testing. Note: These criteria are based upon available regulatory guidance documents. The purpose of the criteria is to specify a threshold of abnormal hepatic tests that may require an additional evaluation for an underlying etiology.

Laboratory test abnormalities: Laboratory abnormalities that constitute an Adverse Event in their own right (are considered clinically significant, induce clinical signs or symptoms, require concomitant therapy or require changes in study treatment), should be recorded. Whenever possible, a diagnosis, rather than a symptom should be provided (e.g. anemia instead of low hemoglobin). Laboratory abnormalities that meet the criteria for Adverse Events should be followed until they have returned to normal or an adequate explanation of the abnormality is found. When an abnormal laboratory or test result corresponds to a sign/symptom of an already reported adverse event, it is not necessary to separately record the lab/test result as an additional event.

Laboratory abnormalities, that do not meet the definition of an adverse event, should not be reported as adverse events. A Grade 3 or 4 event (severe) as per CTCAE does not automatically indicate a SAE unless it meets the definition of serious as defined below and/or as per investigator's discretion. Please note that a dose hold or medication for a lab abnormality may be required by the protocol in which case the lab abnormality would still, by definition, be an adverse event and must be reported as such.

Definition of an Overdose for This Protocol and Reporting of Overdose

For purposes of this trial, an overdose will be defined as any dose exceeding the prescribed dose for MK-3475 by 20% over the prescribed dose.

8.2 Attribution

Assessment of attribution is made by consideration of all clinically relevant data prior to, during, and after occurrence of the event, including diagnostic tests to assess the cause of the event. Clinically relevant data include, but are not limited to; underlying disease, past and present medical history (all concurrent non-malignant disease), concurrent medications, and timing between event and drug administration. The mechanism of action and prior toxicology of the study drug should be considered.

An adverse event is *associated with the use of the drug* when there is a reasonable possibility that the experience may have been caused by the drug. [21CFR312.32(a)]

Attribution Standards per NCI – CTEP:

Unrelated	The Adverse Event is clearly not related to the investigational agent(s)
Unlikely	The Adverse Event is doubtfully related to the investigational agent(s)
Possible	The Adverse Event may be related to the investigational agent(s)
Probable	The Adverse Event is likely related to the investigational agent(s)
Definite	The Adverse Event is clearly related to the investigational agent(s)

8.3 Reporting to Merck

The Principal Investigator will report to Merck in an expedited manner all SAEs meeting the criteria of “serious”, “unexpected” and “related to study treatment”.

For the time period beginning when the consent form is signed until treatment allocation/randomization, any serious adverse event, or follow up to a serious adverse event, including death due to any cause other than progression of the cancer under study that occurs to any subject must be reported within 24 hours to the Sponsor-Investigator and within two (2) working days to Merck Global Safety (GS) if it causes the subject to be excluded from the trial, or is the result of a protocol-specified intervention, including but not limited to washout or discontinuation of usual therapy, diet, placebo treatment or a procedure.

For the time period beginning at treatment allocation/ randomization through 90 days following cessation of treatment, or 30 days following cessation of treatment if the subject initiates new anti-cancer therapy, whichever is earlier, any serious adverse event, or follow-up to a serious adverse event, including death due to any cause other than progression of the cancer under study whether or not related to Merck product, must be reported within 24 hours to the Sponsor-Investigator and within 2 working days to Merck GS.

Additionally, any serious adverse event, considered by an investigator who is a qualified physician to be related to Merck product that is brought to the attention of the investigator at any time following consent through the end of the specified safety follow-up period specified in the paragraph above, or at any time outside of the time period specified in the previous paragraph also must be reported immediately to the Investigator-Sponsor and to Merck GS.

All subjects with serious adverse events must be followed up for outcome.

SAE reports and any other relevant safety information are to be forwarded to the Merck GS [contact].

Reporting of Overdose

No specific information is available on the treatment of overdose of MK-3475. In the event of overdose, MK-3475 should be discontinued and the subject should be observed closely for signs of toxicity. Appropriate supportive treatment should be provided if clinically indicated.

If an adverse event(s) is associated with (“results from”) the overdose of a Merck product, the adverse event(s) is reported as a serious adverse event, even if no other seriousness criteria are met.

All reports of overdose with and without an adverse event must be reported within 24 hours to the Sponsor and within 2 working days hours to Merck Global Safety. (Attn: Worldwide Product Safety; [contact])

Reporting of Pregnancy and Lactation

Although pregnancy and lactation are not considered adverse events, it is the responsibility of investigators or their designees to report any pregnancy or lactation in a subject (spontaneously reported to them that occurs during the trial).

Pregnancies and lactations that occur after the consent form is signed but before treatment allocation/randomization must be reported by the investigator if they cause the subject to be excluded from the trial, or are the result of a protocol-specified intervention, including but not limited to washout or discontinuation of usual therapy, diet, placebo treatment or a procedure/

Pregnancies and lactations that occur from the time of treatment allocation/randomization through 120 days following cessation of Sponsor’s product, or 30 days following cessation of treatment if the subject initiates new anticancer therapy, whichever is earlier, must be reported to the investigator. All reported pregnancies must be followed to the completion/termination of the pregnancy. Pregnancy outcomes of spontaneous abortion, missed abortion, benign hydatidiform mole, blighted ovum, fetal death, intrauterine death, miscarriage and stillbirth must be reported as serious events (Important Medical Events). If the pregnancy continues to term, the outcome (health of infant) must also be reported.

Such events must be reported within 24 hours to the Sponsor and within 2 working days to Merck Global Safety. (Attn: Worldwide Product Safety; [contact])

8.4 Reporting to the Food and Drug Administration

At the discretion of the Principal Investigator, SAEs may be reported to the FDA. Written safety reports will use a MedWatch Form 3500 for voluntary reporting of adverse events, product problems and product use errors. 8.5 Reporting to Yale Human Investigation Committee

Expedited Reporting of Unexpected SAEs

All SAEs meeting the criteria for expedited reporting will be reported to the Yale University Human Investigation Committee (HIC) using HIC Form 6A within 48 hours of discovery.

The Yale University Human Investigation Committee expedited reporting criteria are either:

- a. Serious AND unanticipated AND possibly, probably or definitely related events;
- b. Anticipated Adverse Events occurring with a greater frequency than expected.

8.6 Yale Safety Reporting and Monitoring (DSMP)

The PIs will monitor the clinical trial for safety. The PIs will assess all expedited adverse events and will periodically review all adverse events observed on the trial. Yale Cancer Center standard operating procedures (SOPs) for assessment and reporting of adverse events are followed which are in compliance with 21 CFR 312.32 and 312.22.

The clinical trial data consisting of all required observations, AEs, and laboratory data are entered into a computerized database in a timely manner. The accuracy and completeness of the database, timely submission of SAEs and compliance with the protocol, is assured by periodic auditing conducted by the Yale Cancer Center Data and Safety Monitoring Committee (YCC DSMC). Safety data will be submitted at least once yearly or more often as required by the YCC DSMC. On a regular interval basis, status reports of all laboratory parameters, AEs and SAEs are reviewed by the PI to view composite data across subjects. Regular meetings are held to discuss ongoing patient treatment and adverse events.

Expedited SAE reports submitted by the Investigator to FDA are also copied to the HIC and other relevant institutional safety committees within the timeframes required by Yale. These are also copied to Merck. The Principal Investigator will distribute manufacturer-provided safety reports and updated Toxicity Lists to the institution's HIC and all relevant personnel involved in the conduct of the study. The Toxicity List, in addition to the Investigator's Brochure, will be used as a reference for reporting any new SAE.

Possible actions taken by the PIs or the YCC DSMC if a new unexpected toxicity is identified from the above safety review, or if the periodic review of all adverse events and laboratory data indicates a pattern of incidence or severity of toxicity that raises a safety concern, can be to:

1. Revise consent form
2. Amend the protocol
3. Suspend the protocol

9.0 STATISTICAL ANALYSIS PLAN

In the phase 1b portion of the trial, patients will be enrolled in parallel dose escalation cohorts using the “Rolling Six” method, as described in Section 5.

The primary endpoint of the phase 2a portion of the study is the response rate to post-SBRT MK-3475, separately determined for a NSCLC cohort. A total of 12 patients will be treated at the MTD in the first phase of the study (6 each of lung and non-lung SBRT

targets), and we project that this will include an approximately equal number of NSCLC and melanoma patients. In the second phase of the study, an expansion cohort will be enrolled until a total of 20 NSCLC patients eligible to undergo SBRT is reached (including NSCLC patients treated in the phase I and II portions of the study). We project that approximately 30% of patients (unselected for PD-L1 expression) will respond to the initial MK-3475 for 12 months or more and be replaced. Of those who go on to progress and be SBRT, we estimate that 30% will drop out, or otherwise be ineligible for assessment of response to post-SBRT MK-3475.

There is no published data to suggest a historical control for response to re-treatment with MK-3475, in patients who have been previously treated with MK-3475 and have prior documented progression of disease. In melanoma patients treated with anti-CTLA4 antibody, there is a documented response rate for re-treatment of patients who previously responded and subsequently progressed. In a series of 31 patients who initially had a partial or complete response, and then had progression of disease, re-induction with antibody resulted in a response in 13% of patients. It should be noted, however, that treatment beyond standard RECIST criteria was not permitted in the initial treatment course for these patients, so some may have had pseudoprogression. It is therefore presumed that the expected ORR without SBRT in this population, allowing for treatment beyond RECIST in their initial therapy with MK-3475 is less than 5%. If 4 of 20 patients (20%) in the NSCLC expansion cohort develop a partial or complete response to post-SBRT MK-3475, this strategy will be deemed worth of further investigation. The 95% confidence interval will be (0.05, 0.49) by using one-sample proportion test with continuity correction.

The primary endpoint of this trial will be response rate and the secondary endpoint will be progression-free survival. We will use descriptive statistics to calculate frequency and proportion for the response rate to post-SBRT MK-3475. 95% confidence interval will also be provided. Exact binomial test will be used to compare the observed response rate versus historical control. For the secondary endpoint, we will use Kaplan-Meier estimator to present the progression-free survival.

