Following SBRT, all patients will restart MK-3475 as soon as feasible. They will continue until they have further progression of disease, defined as irPD, or at the discretion of the treating physician if they are felt to receiving clinical benefit.

If MK-3475 is held at any point during a subject's participation in the trial for any reason, the subject will be followed as per standard of care until treatment with MK-3475 is resumed. When treatment with MK-3475 is resumed, the subject will continue with Day 1 procedures for the next planned cycle.

The **phase 2a portion** is an expansion cohort with enrollment closing when 20 NSCLC patients have been enrolled (including those enrolled on phase I). Similar to the phase Ib portion, NSCLC patients who initiated trial therapy on MK-3475 will receive MK-3475 until there is progression of disease (irPD). Patients who do not have progression of disease within that timeframe may continue to receive MK-3475 for up to 18 months per protocol. These patients will not be evaluable for the study endpoints, although their response rates and overall survival will be reported. NSCLC patients will be enrolled after they have irPD on anti-PD-1 therapy received prior to study entry. After progression, an SBRT target will be selected and patients will be treated at the SBRT MTD as determined in the Phase Ib portion of the study, for lung and non-lung targets. The SBRT target will be chosen and ideally SBRT will be delivered as quickly as feasible after the last infusion of MK-3475. In the event of drug-related toxicity or other delay, SBRT may start up to 12 weeks after the last infusion as detailed below in section 5.2.3. Following SBRT, all patients will receive MK-3475 until they develop progression of disease (as defined by irPD), or until they are no longer receiving clinical benefit.

For each phase of the study, the first course of MK-3475 will start on day 1, and will be given every 3 weeks (+/- 7 days) (one cycle). Patients will undergo re-imaging CT of the chest, abdomen, and pelvis at the end of cycle 2, cycle 4, and every 4 cycles thereafter (i.e., at cycles 8, 12, etc.). After the SBRT, when MK-3475 is re-initiated, imaging will be done at the end of cycles 2, 4, and then every 4 cycles. Exceptions to the timing of re-imaging can be made by the treating investigator as necessary to determine course of treatment.

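### The 95% confidence interval printed with the 4-of-20 success rule, (0.05, 0.49), is not what the named method gives; that method gives (0.07, 0.44)

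*Combined protocol and SAP*

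**What the plan says.** Section 9.0 (Statistical Analysis Plan) sets the phase 2a success rule as a count: "If 4 of 20 patients (20%) in the NSCLC expansion cohort develop a partial or complete response to post-SBRT MK-3475", the approach merits further study. The following sentence gives the precision: "The 95% confidence interval will be (0.05, 0.49) by using one-sample proportion test with continuity correction". No other numerator or denominator is attached to that interval.

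Three other statements bear on it.

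- **Reference rate.** The same section presumes that the response rate without SBRT, "allowing for treatment beyond RECIST in their initial therapy with MK-3475 is less than 5" per cent.
- **Cohort size.** Section 9.0 enrols "until a total of 20 NSCLC patients eligible to undergo SBRT is reached", and Section 5.2.1 has "enrollment closing when 20 NSCLC patients have been enrolled". Section 9.0 also says of patients who go on to SBRT that "we estimate that 30% will drop out, or otherwise be ineligible for assessment of response to post-SBRT MK-3475".
- **Final analysis.** Section 9.0 promises a 95% confidence interval without naming its method, and adds: "Exact binomial test will be used to compare the observed response rate versus historical control".

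**The concern.** Section 9.0 supplies everything needed to recompute the interval: 4 responders, 20 patients, 95% and a named method. The result is not the printed pair, and an upper limit of 0.49 against 0.44 is too far off to be rounding.

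This is the only precision figure beside the primary success rule, so it is what a reader will use to judge how much a just-successful result would show. As printed, the lower limit sits on the 5% reference rate, which suggests that 4 of 20 would barely fail to exclude it. The correct lower limit is above 5%.

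The mismatch also raises the question of whether the interval was computed for a different number of patients from the 20 in the rule. The plan itself expects fewer than 20 of the SBRT patients to be assessable for response.

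**Working it through.** **Inputs (all from Section 9.0).** x = 4 responders, n = 20, so p = 0.20; 95% level, taken as two-sided (z = 1.960, z² = 3.8415) because sidedness is not stated; continuity-corrected one-sample proportion method; reference rate 5%; 30% of SBRT patients lost to response assessment.

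**Step 1. Try to reproduce the printed figure.** The interval belonging to the continuity-corrected one-sample proportion test is the score (Wilson) interval with p moved outward by 0.5/n:

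limit = [p* + z²/(2n) ± z·√(p*(1 − p*)/n + z²/(4n²))] / (1 + z²/n)

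with p* = p − 0.5/n for the lower limit and p + 0.5/n for the upper. For n = 20: 0.5/n = 0.025, z²/(2n) = 0.0960, z²/(4n²) = 0.00240, 1 + z²/n = 1.1921.

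- Lower: p* = 0.175. Root = √(0.175 × 0.825/20 + 0.00240) = √0.00962 = 0.0981. Limit = (0.175 + 0.0960 − 1.960 × 0.0981)/1.1921 = 0.0788/1.1921 = 0.066.
- Upper: p* = 0.225. Root = √(0.225 × 0.775/20 + 0.00240) = √0.01112 = 0.1055. Limit = (0.225 + 0.0960 + 1.960 × 0.1055)/1.1921 = 0.5277/1.1921 = 0.443.

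The result is (0.0661, 0.4427), or (0.07, 0.44). The printed (0.05, 0.49) is not reproduced.

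**Step 2. Try other methods for 4 of 20.**

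| 95% interval for 4/20 | Lower | Upper |
|---|---|---|
| Printed | 0.05 | 0.49 |
| Score, corrected (named method) | 0.066 | 0.443 |
| Score, uncorrected | 0.081 | 0.416 |
| Clopper-Pearson | 0.057 | 0.437 |
| Wald | 0.025 | 0.375 |
| Wald, corrected | 0.000 | 0.400 |
| Agresti-Coull | 0.075 | 0.422 |
| Jeffreys | 0.072 | 0.408 |

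None matches, and the 90% and 99% versions do not either.

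**Step 3. Size of the error.** Correct width: 0.4427 − 0.0661 = 0.3766. Printed width: 0.49 − 0.05 = 0.44. Ratio: 0.44/0.3766 = 1.168, so about 17% too wide. The printed limits are rounded to two decimals, so the width behind them could be 0.43 to 0.45. The ratio then runs from 0.43/0.3766 = 1.14 to 0.45/0.3766 = 1.19.

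**Step 4. Which count would give the printed pair?** Every whole-number count with n from 5 to 80 was tried under the corrected score, uncorrected score and Clopper-Pearson methods. Only 3/15 by the corrected score method, (0.053, 0.486), rounds to (0.05, 0.49). None truncates to it. Three of 15 is also 20%, but the plan mentions no group of 15, so this origin is probable and not documented.

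**Step 5. The denominator implied by the plan's own loss estimate.** 20 × 0.7 = 14. The named method gives (0.025, 0.438) for 2/14 and (0.057, 0.512) for 3/14. Entering exactly 20% of 14, or 2.8 responders, gives (0.050, 0.498), which rounds to (0.05, 0.50).

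**Step 6. Does the decision rule depend on the interval?** For 20 patients and a 5% rate, P(X ≥ 4) = 1 − (0.3585 + 0.3774 + 0.1887 + 0.0596) = 0.016. This calculation and the count rule do not use the interval.

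**The case against.** The strongest reply is that the interval may have been computed for the patients expected to be assessable, not for all 20. The plan's own figures give 14, and the named method at 20% of 14 gives (0.0501, 0.4976), which truncates to the printed pair. A planning interval at an expected rate does not strictly need a whole-number count. On that reading the interval is roughly right and the fault is an unlabelled denominator. Substituting (0.07, 0.44) would then overstate precision by ignoring the 30% loss.

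Part of this stands: a denominator below 20 is a real possibility, and it should be settled before the pair is changed. It does not rescue the sentence. The interval directly follows a rule stated as 4 of 20, 2.8 responders cannot be observed, and ordinary rounding gives 0.50 for the upper limit.

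It is also fair to say that the consequence is small. The rule is a count, the test is exact, the reported interval will come from the observed data, and the printed one errs on the wide side. The plan draws no comparison between the lower limit and 5%, so the risk of misreading is a judgement. These points limit the importance of the error but leave the figure wrong.

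**Conclusion.** The concern holds. For 4 of 20 by the named method the 95% interval is (0.066, 0.443), not (0.05, 0.49). The lower limit is printed 0.016 too low and the upper limit about 0.047 too high, and the width is about 17% too large (14% to 19% allowing for rounding of the printed limits).

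This rests on a two-sided interval and on 20 as the denominator, as the success rule states. If 20 is right, the threshold, the exact test (P = 0.016 against 5%) and the sample size are unaffected, and only planning precision is misstated, in the direction of understating it. If a smaller number of assessable patients was intended, the interval may be closer to right, but the rule then no longer fits: 4 of 14 is 29%, not 20%. The correction should be made, but it does not alter the design.

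**What to change.** 1. Confirm that 20 is the number of response-assessable NSCLC patients on which the success rule and the interval are based.
2. If it is, keep the named method in Section 9.0 and replace (0.05, 0.49) with (0.07, 0.44). Optionally, give the Clopper-Pearson interval (0.06, 0.44) and rename the method, to match the planned exact binomial test. This is a preference; a score interval beside an exact test is not an error.
3. If a smaller denominator was intended (for example 15, or the 14 left after the projected loss), state it and reconcile the cohort size, the threshold of 4 and the interval.

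If 20 is confirmed, the cost is one number pair in one sentence, with no additional patients or data. If a smaller number was intended, the rule and the cohort size also need revisiting.
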